6. BENEFIT:RISK ASSESSMENT

6.1. Benefit Assessment

The efficacy of baricitinib in subjects with GCA has not yet been established. However, available pre-clinical data provide rationale for the use of JAK inhibitors in GCA. Furthermore, baricitinib has been shown to be safe and effective in patients with rheumatoid arthritis. Glucocorticoids are the current standard of care treatment for GCA. However, prolonged use with GCs is associated with significant risk of adverse events. This study, if successful, will provide preliminary evidence that may result in a new therapy for GCA where there remains a clear unmet need.

Subjects will be receiving standard of care treatment with GC during the study period, albeit with a quicker taper than is typically followed in clinical practice. Subjects will receive high level of care throughout the study and will benefit from the frequent physical examinations and frequent monitoring of vital signs and blood tests.

6.2. Risk Assessment

There are currently no known contraindications or identified risks requiring special warnings or special precautions for use of Baricitinib. Potential risks have been identified and are detailed in the included accompanying Investigator Brochure for Baricitinib (LY3009104). Potential risks are summarized below.

Increased Adverse Events Due to Increased Exposures in Patients with Renal Impairment:

Data from completed studies indicate that subjects with renal impairment have increased exposure to baricitinib. Increased exposure could place a person at increased risk for any other risk that is related to exposure. Investigators will follow dosing guidelines specified in the protocol, and monitor creatinine in study subjects and follow protocol drug interruption and discontinuation criteria.

Myelosuppression: Baricitinib is anticipated to down-regulate the JAK pathway and result in changes to white blood cell counts. Although dose-related decreases in neutrophils and other phagocytic cell lines have been observed, neutropenia and lymphocytopenia have been observed infrequently. Investigators will monitor leukocyte parameters in study subjects and follow protocol drug interruption and discontinuation criteria.

Increased Infections (including opportunistic infections and herpes zoster): In addition to the observed decreases in phagocytic cells, JAK inhibition down-regulates cytokines related to the immune system. Although infections and infestations were the most frequently reported treatment emergent adverse event (TEAE) occurrence of infections typically considered to be opportunistic has not been observed in clinical studies with baricitinib. The incidence rate of herpes zoster observed in baricitinib studies is within the range reported in observational studies and clinical trials of patients with RA. Investigators will monitor subjects for clinical signs and symptoms of infectious events, including herpes zoster. If a subject is clinically diagnosed with herpes zoster, the investigator will interrupt investigational product, initiate standard of care

(including antiviral therapy and relevant supportive care as appropriate), monitor for multi-dermatomal involvement or other evidence of dissemination, and follow subjects until clinical recovery of skin lesions (vesicles).

Increased Cardiovascular Events Due to Changes in Lipids: Increases in mean total cholesterol, LDL, HDL, and triglycerides have been noted in studies with baricitinib. Nuclear magnetic resonance data indicate that the changes in cholesterol are due primarily to increases in the number of HDL particles without a change in HDL particle size; an increase in the number of large LDL particles with no significant increases in small, medium-small or very small LDL particles; and an increase in the number of total, as well as medium and small, very low density lipoprotein particles. The mean values for the HDL/LDL ratio did not change. These changes in lipid particles, particularly in view of the observed increase in large LDL particles, suggest that the overall effect on the vasculature may not be atherogenic. Any increase in cholesterol carries a potential risk of cardiovascular events. Data from patients with rheumatoid arthritis given 4 to 15 mg baricitinib QD or 5 mg baricitinib BID have shown no clinically meaningful changes in vital signs or ECG parameters for baricitinib versus placebo. Investigators will monitor for change in lipid profile from baseline to week 16 to assess for the development of hyperlipidemia. If present then institution of hyperlipidemia medications will be suggested if clinically recommended.

Fetal Malformations: Reproductive toxicity was observed in rat and rabbit toxicology studies, including maternal toxicity and skeletal malformations in the rat fetus. A decrease in mating performance (fertility and copulation indices) was observed in the male rat fertility study. This change occurred without effects on spermatogenesis as assessed by histopathology and semen/sperm endpoints. Pregnant women will not participate in this study. To manage risks, women of reproductive potential should avoid becoming pregnant by using 2 forms of highly effective contraceptives while participating in clinical studies and for 28 days following exposure to baricitinib. Screening for pregnancy will occur during the screening period and at all study visits. The population affected by GCA has an average diagnosis age of 72, therefore the likelihood of patients being of childbearing age is of low likelihood.

Emergence of Malignancies Previously Contained by the Immune System: Baricitinib has immunomodulatory effects on the immune system. Effects on the immune system may permit emergence of malignancies previously contained by the immune system. No signals concerning effects of baricitinib on malignancy have emerged from clinical studies. Patients should be monitored closely for evidence of neoplasia or malignancy, and study drug should be discontinued if such events occur.

Accelerated Prednisone Taper: In addition to the information available for Baricitinib, a quicker taper of steroids may lead to withdrawal side effects. Subjects may experience GCA relapse during steroid taper. Inclusion of subjects with stable disease on study entry who are able to safely participate in the steroid taper and have had duration of steroids \leq 4 years. Monitoring of subjects during steroid taper and following discontinuation. Subjects with severe ischemic manifestations related to GCA will be excluded from the trial. Disease relapses will be treated with increased dose of GCs.

6.3. Overall Benefit:Risk Conclusion

While the efficacy of baricitinib in subjects with GCA is unknown, pathophysiologic rationale exists to consider use in GCA, given that baricitinib has been shown to be safe and effective in rheumatoid arthritis.

Taking into account the measures taken to minimize risk to subjects participating in this study, the potential risks identified in association with baricitinib are justified by the anticipated benefits that may be afforded to subjects with GCA. If baricitinib is able to sustain a GC-free remission this would significantly reduce the burden of GC-related toxicity, which is commonly encountered in long term management of subjects with GCA.

7. SELECTION OF STUDY POPULATION AND WITHDRAWAL CRITERIA

7.1 Inclusion Criteria

Subjects are eligible for enrollment in the study if the following inclusion criteria are met:

1. Diagnosis of GCA defined by the following Revised GCA Diagnosis Criteria:

- Age ≥ 50 years.
- History of ESR ≥ 50 mm/hour or CRP ≥ 10 mg/L.
- Presence of at least **one** of the following:
 - Unequivocal cranial symptoms of GCA (new onset localized headache, scalp or temporal artery tenderness, otherwise unexplained mouth or jaw pain upon mastication).
 - Unequivocal symptoms of PMR, defined as shoulder and/or hip girdle pain associated with inflammatory stiffness.
 - Systemic inflammatory disease in which the presence of the fever (>38 degrees Celsius for ≥ 7 days), weight loss (> 5 lbs or 10% pre-morbid weight), and/or night sweats were attributable to GCA and no other cause was identified.
- Presence of at least **one** of the following:
 - Temporal artery biopsy revealing features of GCA.
 - Evidence of large-vessel vasculitis by angiography or cross-sectional imaging, including but not limited to magnetic resonance angiography (MRA), computed tomography angiography (CTA), positron emission tomography-computed tomography (PET-CT) or evidence of large-vessel or temporal artery vasculitis by ultrasound (US).

2. Relapse with active GCA within 6 weeks of study entry where active disease is defined by an ESR ≥ 30 mm/hr or CRP ≥ 10 mg/L AND the presence of at least **one**

of the following:

- Unequivocal cranial symptoms of GCA (new onset or recurrent localized headache, scalp or temporal artery tenderness, otherwise unexplained mouth or jaw pain upon mastication [i.e., jaw claudication]).
- Unequivocal symptoms of PMR, defined as shoulder and/or hip girdle pain associated with inflammatory stiffness.
- Other feature(s) judged by the clinician investigator to be consistent with GCA or PMR flares (e.g. fever of unknown origin, weight loss, fatigue/malaise, etc.)

3. Clinically stable at baseline visit (study drug initiation) such that the subject is able to safely participate in the standardized taper regimen in the opinion of the investigator.

7.2. Exclusion Criteria

A subject will not be eligible for inclusion in this study if any of the following criteria apply:

1. Presence of any other autoimmune disease (such as systemic lupus erythematosus, rheumatoid arthritis, inflammatory arthritis, other vasculitides, scleroderma, polymyositis, dermatomyositis, or other similar systemic connective tissue diseases).
2. Subjects demonstrating symptoms of active or newly developing visual loss (transient or permanent blindness) or diplopia attributable to GCA at the time of relapse. Patients with history of visual ischemia present at the time of original GCA diagnosis will still be considered eligible if at the time of the documented pre-study relapse there is no evidence of change/progression of their known visual deficit that can be attributed to active GCA.
3. Subjects with history of aortic dissection, myocardial infarction, or cerebrovascular attack attributable to GCA.
4. Has received, or is expected to receive, any live virus vaccinations (with the exception of herpes zoster vaccination) within 3 months before the first dose of study drug, during the study, or within 3 months after the last administration of the study drug. All patients who have not received the herpes zoster vaccine at screening will be encouraged (per local guidelines) to do so prior to randomization; vaccination must occur >4 weeks prior to randomization and start of investigational product. Patients will be excluded if they were exposed to herpes zoster (Zostavax) vaccination within 4 weeks of planned randomization. Patients may receive the inactivated (non-live) herpes zoster vaccine (Shingrix) at any time prior to or after the study start.
5. Organ transplant recipients.
6. Have had a major surgery within 8 weeks prior to screening or will require major surgery during the study that, in the opinion of the investigator would pose an unacceptable risk to the patient.
7. Have experienced any of the following within 12 weeks of screening: myocardial infarction (MI), unstable ischemic heart disease, stroke, or New York Heart Association Stage IV heart failure
8. Have a history or presence of cardiovascular (including but not limited to uncontrolled hypertension), respiratory, hepatic, gastrointestinal, endocrine, hematological, neurological, or neuropsychiatric disorders, or any other serious and/or unstable illness that, in the opinion of the investigator, could constitute an unacceptable risk when taking investigational product or interfere with the interpretation of data.
9. Are largely or wholly incapacitated permitting little or no self-care, such as being bedridden or confined to a wheelchair.
10. Have an estimated glomerular filtration rate (eGFR) of <50 mL/min/1.73 m².
11. Have a known history of chronic liver disease with the most recent available aspartate aminotransferase (AST) or alanine aminotransferase (ALT) > 2 times the upper limit of normal (>2 x ULN)
12. Known evidence of hyperbilirubinemia with a prior total bilirubin ≥ 1.5 x ULN.
13. Have a history of lymphoproliferative disease; or have signs or symptoms suggestive of possible lymphoproliferative disease, including lymphadenopathy or splenomegaly; or have active primary or recurrent malignant disease; or have been in remission from clinically significant malignancy for < 5 years.
 - a. Subjects with uterine cervical carcinoma in situ that has been resected with no evidence of recurrence or metastatic disease for at least 3 years may participate in the study
 - b. Subjects with basal cell or squamous epithelial skin cancers which have been completely resected with no evidence of recurrence for at least 3 years may participate in the study.
14. Active infections, or history of recurrent infections or have required management of acute or chronic infections as evidenced by any of the following:

- a. Currently on any suppressive therapy for a chronic infection (such as tuberculosis, cytomegalovirus, herpes simplex, herpes zoster, or atypical mycobacteria).
 - b. History or suspicion of chronic infection (e.g. prosthetic joint infection)
 - c. Hospitalization for treatment of infection within 60 days of baseline visit
 - d. Use of parenteral (IV or IM) antimicrobials (antibacterial, antifungals, antivirals, or antiparasitic agents) within 60 days of baseline or oral antimicrobials within 30 days of baseline visit for treatment of an active infection. This does not include the use of antibiotics for prophylaxis against pneumocystis pneumonia since this is considered standard of care for patients on prednisone ≥ 20 mg/day for longer than 3 consecutive months.
15. Have had symptomatic herpes zoster infection within 12 weeks prior to screening.
 16. Have a history of disseminated/complicated herpes zoster (for example, multidermatomal involvement, ophthalmic zoster or CNS involvement)
 17. In the opinion of the investigator, are at an unacceptable risk for participating in the study.
 18. Have known or documented diagnosis of human immunodeficiency virus (HIV).
 19. Have known or documented primary immunodeficiency.
 20. Have had household contact with a person with active tuberculosis (TB) and did not receive appropriate and documented prophylaxis for TB.
 21. Have had evidence of active TB or have previously had evidence of active TB and did not receive appropriate and documented treatment.
 22. Have evidence of latent TB as documented by a local lab positive QuantiFERON®-TB Gold test and a normal chest x-ray, unless a patient completes at least 4 weeks of appropriate treatment prior to study entry and agrees to complete the remainder of treatment while in the trial.
 - a. If the QuantiFERON®-TB Gold test results are positive, the patient will be considered to have latent TB and will be excluded, unless treatment is initiated as outlined above. If the test is indeterminate, the test may be repeated once within 2 weeks of the initial value with either a second QuantiFERON®-TB Gold Test or with a different interferon gamma release assay (i.e. T-Spot tuberculosis test).. If the second test result is again not negative (i.e. positive or indeterminate), the subject will be considered to have latent TB (for purposes of this study) and will be excluded, unless treatment is initiated as outlined above.
 - b. Exceptions include subjects with a history of active or latent TB who have documented evidence of appropriate treatment and with no history of re-exposure since their treatment was completed. (Such subjects would not be required to undergo the protocol specific TB testing, but would require a baseline chest x-ray).
 23. Have a positive test for HBV defined as:
 - a. Positive for hepatitis B surface antigen (HBsAg), or
 - b. Positive for anti-hepatitis B core antibody (HBcAb)
 If any of the HB tests have an indeterminate result, confirmatory testing will be performed by an alternate method.
 24. Have HCV (positive for anti-hepatitis C antibody with confirmed presence of HCV).
 25. Have any of the following specific abnormalities at time of relapse or during screening:
 - a. ALT or AST $> 2 \times$ ULN
 - b. Hemoglobin < 10 g/dL
 - c. Total white blood cell count (WBC) < 2500 cells/ μ L)
 - d. Neutropenia (absolute neutrophil count [ANC] < 1200 cells/ μ L)
 - e. Lymphopenia (lymphocyte count < 750 cells/ μ L)
 - f. Thrombocytopenia (platelets $< 100,000$ cells/ μ L)
 - g. eGFR < 50 mL/min/1.73m²

In the case of any of the aforementioned laboratory abnormalities, the tests may be repeated once within approximately 2 weeks from the initial values, and values resulting from repeat testing may be accepted for enrollment eligibility if they meet the eligibility

criterion.

26. Are pregnant or breast feeding at the time of screening or enrollment.
27. Are females of childbearing potential who do not agree to use 2 forms of highly effective birth control when engaging in sexual intercourse with a male partner while enrolled in the study and for at least 4 weeks following the last dose of the study drug
 - a. Females of non-childbearing potential are defined as women ≥ 60 years of age, women ≥ 40 but < 60 years of age what had had cessation of menses for at least 12 months, or whom who are congenitally or surgically sterile (that is have had a hysterectomy, or bilateral oophorectomy or tubal ligation)
 - b. The following birth control methods are considered highly effective (the subject should choose 2 to be used with their male partner)
 - i. Oral, injectable, or implanted hormonal contraceptives
 - ii. Condom with spermicidal foam, gel film, cream or suppository
 - iii. Occlusive cap (diaphragm or cervical/vault caps) with a spermicidal foam, gel, film, cream or suppository
 - iv. . Intrauterine device
 - v. Intrauterine system (for example progestin-releasing coil)
 - vi. Vasectomies male (with appropriate post-vasectomy documentation of the absence of sperm in the ejaculate)
28. Are males who do not agree to use 2 forms of highly effective birth control (see above) while engaging in sexual intercourse with females partners of childbearing potential while enrolled in the study and for 4 weeks after the last dose of the study drug.
29. Have donated more than a single unit of blood within 4 weeks prior to screening or intend to donate blood during the course of the study.
30. Have a history of chronic alcohol abuse, IV drug abuse, or other illicit drug abuse within the 2 years prior to screening.
31. Have previously received baricitinib for other investigational study.
32. Are unable or unwilling to make themselves available for the duration of the study and/or are unwilling to follow study restrictions/procedures
33. Are currently enrolled in, or discontinued within 4 weeks prior to screening from any other clinical trial involving an investigational product or nonapproved use of a drug or device or concurrently enrolled in any other type of medical research judged not to be scientifically or medically compatible with this study.
34. Are investigator site personnel directly affiliated with this study and/or their immediate families. Immediate family is defined as a spouse, parent, child, or sibling whether biological or legally adopted.
35. Have a chronic medical illness requiring the use of oral or IV glucocorticoid treatment (e.g. asthma or emphysema) during the trial or requiring long term glucocorticoid treatment such that they would not be able to safely undergone a standardized glucocorticoid taper.

7.3. Excluded Prior/Concomitant Therapy

Had prior treatment with any of the following:

- Systemic immunosuppressives, including azathioprine, oral cyclosporine A, tacrolimus, mycophenolate mofetil and IL-1ra (anakinra) within 4 weeks of baseline.
- Leflunomide within 12 weeks of baseline
- Methotrexate within 2 weeks of baseline
- Etanercept within 4 weeks or within 8 weeks of baseline with adalimumab, certolizumab, golimumab, infliximab
- Cyclophosphamide within 8 weeks of baseline

- Received any anti-IL6 agent (tocilizumab, sirukumab, sarilumab) and had failure to control GCA symptoms (i.e. primary therapeutic failure) at any point prior to study screening/entry.
 - Patients having received an anti-IL6 agent that were intolerant to the medication (e.g. injection site or infusion reaction) may still be considered eligible for study enrollment.
 - Patients for which an IL-6 agent is being stopped for reason other than therapeutic failure are also considered eligible for study enrollment.
 - Prior to baseline visit/study drug initiation, the patient must be off of the anti-IL6 agent for 4 weeks prior to baseline for infusible (intravenous) formulations and 2 weeks prior for subcutaneously administered formulations.
- Rituximab within 12 months of baseline or longer if B cell counts have not returned to normal range or baseline levels
- Abatacept within 8 weeks of baseline
- Tofacitinib at any point prior to study screening/entry
- Intravenous (pulse) doses of glucocorticoid defined as methylprednisolone > 100 mg/day within 8 weeks of baseline
- Probenecid within 2 weeks of baseline visit

8. **STUDY TREATMENT**

8.1 **Investigational Product**

	Study Treatment
Product name	Baricitinib
Dosage form	Tablet
Unit dose	4 mg
Route of administration	Oral
Dosing instruction	Daily

The term “study drug” and “study treatment” are used throughout the protocol to describe the investigational product received by the subject per protocol design (i.e. baricitinib 4 mg oral tablet).

Baricitinib will be supplied by Eli Lilly [investigational product (IP) manufacturer]. The tablets are composed of baricitinib free base and the inactive ingredients microcrystalline cellulose, mannitol, croscarmellose sodium and magnesium stearate. Each tablet contains baricitinib equivalent to 4 mg of the free base compound. The supplied tablets will be held at the Mayo Clinic Outpatient Research Pharmacy during the duration of the study and dispensed to the patient at each scheduled visit with sufficient doses until the subsequent scheduled visit. The maximum amount of supply provided will be 2 months. The medication will be stored according to specification on the label. Patients will keep a diary of all days on which baricitinib is taken to assess compliance at each study visit.

9. **STUDY PROCEDURES**

9.1. **Recruitment**

Recruitment will occur through the clinical practices of the investigators at the study site. Subject enrollment at the study site will not occur until Institutional Review Board (IRB) approval of this protocol and the informed consent form (ICF) has been obtained. Details of the goals of the research and the risk and benefits of the protocol will be reviewed with each potential study subject. Recruitment will occur by physicians or study coordinators.

Subjects who decline participation will continue to be followed by their current physician as deemed appropriate.

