Safety and efficacy data will be collected at the time of each clinical visit. In the absence of disease worsening, relapse, or drug toxicity, subjects will continue baricitinib for 52 weeks. Following completion of 52 weeks of treatment, all subjects will discontinue baricitinib. For safety purposes a follow-up visit will occur 12 weeks after discontinuation of the study drug for all

subjects, including those with earlier study drug withdrawal.

The maximum duration of subject participation (including screening) is 70 weeks. Completion of the study is defined as completion of the 52-week treatment period and 12-week follow-up visit.

TABLE 1: Standardized prednisone taper

Time (Week)	Prednisone dose and tapering schedule		
Screening: -6 to -2*	30	20	10
0	30	20	10
1	25	17.5	9
2	22.5	15	8
3	20	12.5	7
4	17.5	10	6
5	15	9	5
6	12.5	8	5
7	10	7	4
8	9	6	4
9	8	5	3
10	7	5	3
11	6	4	2
12	5	4	2
13	5	3	1
14	4	3	1
15	4	2	0
16	3	2	
17	3	1	
18	2	1	
19	2	0	
20	1		
21	1		
22	0		

*subjects must be on stable dose of either 30 mg, 20 mg, or 10 mg for 2 weeks prior to baseline (week 0)

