5.3. Treatment Arms and Duration

This is an open-label, single-arm study. All subjects will receive the study drug for a maximum of 52 weeks in combination with a standardized prednisone taper.

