9.6. Visit Frequency/Visit Schedule

Subjects will be evaluated for potential eligibility. Once eligibility is deemed likely, they will be consented and undergo screening. Labs pertaining to determination of eligibility will be obtained during the screening period [QuantiFERON-TB, Hepatitis panel, pregnancy test (if applicable)]. If standard of care labs (complete blood count, inflammatory markers, creatinine, transaminases) were performed at time of observed relapse these will be used for assessment of their respective eligibility laboratory parameters. If they were not drawn at time of observed relapse they will be drawn during the screening period. Standard of care labs will be obtained at each follow up visit, including the 12-week post treatment visit (W64). Lipid profiles will be obtained at week 0 and week 16.

Imaging can be performed in the study period with non-invasive angiography if clinically indicated and is

not considered a requirement for screening or necessary for study enrollment. Computed tomography angiography (CTA) and magnetic resonance angiography (MRA) is recommended at time of diagnosis for patients with GCA (level of evidence Class I, Level C) [41]. If large vessel involvement is observed on advanced imaging, follow up scan at 12-15 months is recommended.

Upon enrollment (Week 0), the study drug will be initiated and standardized GC taper begun. A follow-up visit will occur at week 4 (W4), week 8 (W8), then every 8 weeks until week 52 (W52) when study drug will be discontinued. After study drug is completed a 12-week follow up visit will occur (W64).

Visit dates can be ± 4 days from the assigned week to allow for subject travel and investigator availability. A summary of the visit schedule can be seen in the **Table 2**.

Table 2: Visit Schedule

Study Date W=Week (± 4 days)	Observed Relapse	Screening (up to 42 days)	W0	W4	W8	W16	W24	W32	W40	W52	W64
Study drug initiation			X								
Prednisone taper initiation			X								
Office visit	X		X	X	X	X	X	X	X	X	X
Data Forms											
Informed consent	X										
Eligibility review	X	X	X								
Demographics		X									
Baseline medical history		X									
Medications		X									
Tobacco use		X									
Patient Global Assessment			X	X	X	X	X	X	X	X	X
Physician Global Assessment			X	X	X	X	X	X	X	X	X
Vascular Damage Index			X							X	
Birmingham Vasculitis Activity Score			X	X	X	X	X	X	X	X	X
Imaging											
CTA or MRA Chest ^d		X									
Labs											
Hepatitis panel ^b		X*									

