11. STUDY ENDPOINTS

Primary endpoint:	
The primary endpoint is safety.
 
The measure by which this will be determined is the following:
 
 • Incidence of adverse events (AEs) and serious adverse events (SAEs) related to the study drug
Secondary endpoint	
The secondary endpoint preliminary efficacy of baricitinib (4mg, oral, daily) in patients with relapsing GCA.
 
The measures by which this will determined are the following:

	
 • Relapse-free survival at week 52 • Relapse-free survival at week 24 • Duration of glucocorticoid-free remission • Number of relapses per subject over time • Change from baseline erythrocyte sedimentation rate (ESR) to end of study • Change from baseline C-reactive protein to end of study • Glucocorticoid dose (mg) at week 52 compared to enrollment • Change in BVAS from baseline to end of study
--	---

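### Section 8.1's two dispensing rules cannot both be met at W40: Table 2 leaves 84 days to W52 against a 2-month supply cap, and Section 9.6 implies a W48 visit that Table 2 lacks

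*Combined protocol and SAP*

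**What the plan says.** Section 8.1 (Investigational Product) sets two rules for study drug. Tablets are "dispensed to the patient at each scheduled visit with sufficient doses until the subsequent scheduled visit". The next sentence limits the quantity: "The maximum amount of supply provided will be 2 months". Two months is not expressed in days or tablets. No section describes a refill between visits, and none forbids one. Section 8.1 also creates a dosing record: "Patients will keep a diary of all days on which baricitinib is taken to assess compliance at each study visit".

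Section 9.6 gives the visit schedule twice. The text reads: "A follow-up visit will occur at week 4 (W4), week 8 (W8), then every 8 weeks until week 52 (W52". Table 2, introduced as a summary of the schedule, has columns for W0, W4, W8, W16, W24, W32, W40, W52 and W64. Each visit may move by plus or minus "4 days from the assigned week to allow for subject travel and investigator availability".

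Dosing is one 4 mg tablet daily (Sections 5.6.1 and 8.1). On duration, Section 5.2 says: "In the absence of disease worsening, relapse, or drug toxicity, subjects will continue baricitinib for 52 weeks". Section 5.3 says: "All subjects will receive the study drug for a maximum of 52 weeks".

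**The concern.** Each rule in Section 8.1 is reasonable alone. Together they work only if no interval between visits is longer than the cap, and the last on-treatment interval in Table 2 is 12 weeks. At W40 the pharmacy must either break the cap or hand out too few tablets to reach W52, and the text does not say which rule yields. The Section 9.6 sentence does not settle it, because it describes a different schedule from the table.

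What is at stake is continuity of treatment just before the week-52 assessment. Under Table 1, subjects without relapse reach zero prednisone at week 15, 19 or 22, depending on entry dose. If baricitinib also ran out before W52, they would be on neither drug for the last weeks of the treatment period. Relapse-free status at week 52 would then mix on-drug and off-drug time, although Section 5.2 intends drug throughout. With 15 subjects, one relapse in that stretch moves the proportion by 1/15 = 6.7 percentage points.

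**Working it through.** The cap is an operational rule, so the plan has no derived figure to reproduce. The check is calendar arithmetic at one tablet per day.

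**Inputs.** Visit weeks from Table 2; a window of 4 days either side from Section 9.6; both dispensing rules from Section 8.1. Assumption: two calendar months are 59 to 62 days. A reading as 8 weeks (56 days) is shown separately.

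**1. Intervals in Table 2** (7 × difference in weeks): 28, 28, 56, 56, 56, 56 and 84 days. The last is W40 to W52, day 280 to day 364.

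**2. W40 to W52 with windows.** W40 falls on days 276 to 284 and W52 on days 360 to 368.
- Shortest: 360 − 284 = 76 days.
- Longest: 368 − 276 = 92 days.

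The shortest interval (76) exceeds the most generous cap (62) by 14 days, so no reading of 2 months and no use of the windows satisfies both rules at W40.

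**3. The Section 9.6 wording.** Steps of 8 weeks from W8 give W16, W24, W32, W40 and W48. W52 is not on that grid: (52 − 8)/8 = 5.5. With W48 included and W52 as the end of treatment, the intervals are 28, 28, 56, 56, 56, 56, 56 and 28 days. The longest is 56 days, so both rules are met at nominal dates. With windows, an 8-week interval can reach 64 days and exceed the cap by 2 to 5 days (8 if 2 months means 56 days).

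**4. Shortfall if the cap were enforced at W40 with no refill and no saved tablets.**

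| 2 months read as | Days short at nominal dates | Share of 364 days | Supply ends |
|---|---|---|---|
| 62 days | 84 − 62 = 22 | 6.0% | day 342 |
| 59 days | 84 − 59 = 25 | 6.9% | day 339 |
| 56 days (8 weeks) | 84 − 56 = 28 | 7.7% | day 336 |

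**5. Saved surplus.** Suppose a full 2-month supply is given at every visit before W40 and leftovers are kept.
- W0 and W4 (28-day intervals): 2 × (59 − 28) = 62 to 2 × (62 − 28) = 68 tablets; 2 × (56 − 28) = 56 under the 8-week reading.
- W8, W16, W24 and W32 (56-day intervals): 4 × (59 − 56) = 12 to 4 × (62 − 56) = 24 tablets; 0 under the 8-week reading.
- Total: 74 to 92, or 56 under the 8-week reading.

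Every total exceeds the matching shortfall of 22 to 28 tablets, so carry-over on that scale closes the gap completely.

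**The case against.** The strongest reply is that the documents show no drug gap. Section 8.1 itself requires enough tablets to reach the next visit, and Sections 5.2 and 5.6.1 require 52 weeks of treatment. A gap arises only if staff enforce the cap against those requirements. Tablets are kept at the site's own research pharmacy, and surplus from W0 and W4 alone could cover the shortfall. This stands: the loss of drug is conditional, and a reader who infers that subjects will go untreated before W52 goes beyond the text. It does not remove the conflict, because overriding the cap departs from the written protocol and the text describes neither a refill nor accumulation of surplus.

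A second reply is that Section 9.6 calls Table 2 a summary, so the text may govern and a W48 column may have been left out. That is possible, and it would resolve the conflict. The documents do not say which source takes precedence. The missing W48 does not look like a fault in reading the table: rows marked at every visit, such as the global assessments and BVAS, carry nine marks for the nine columns W0 to W64.

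Two stronger inferences should be resisted.

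- A reader might conclude that the change in ESR, CRP and BVAS would also be measured off drug because of this conflict. The documents do not settle that. Those measures run to the end of study, which Section 9.12 ties to the last subject's last visit, and a completed subject has attended W64. If W64 is meant, they are off drug by design.
- A reader might conclude that the primary safety assessment is compromised. The Section 11 measure is "Incidence of adverse events (AEs) and serious adverse events (SAEs) related to the study drug", and Section 12.6 collects events from the start of treatment to the 12-week follow-up whatever the tablet supply. Laboratory draws from W4 to W40 precede any gap.

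**Conclusion.** The inconsistency is real and does not depend on how 2 months is read. With Table 2 as the schedule, the two rules in Section 8.1 cannot both be followed at W40, and Section 9.6 describes a schedule that Table 2 does not contain.

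The consequence is conditional on strict enforcement of the cap, no refill and no carried-over tablets. It would then be about three and a half weeks without drug, immediately before W52. A longer figure requires the 8-week reading or unfavourable visit windows. Week-52 relapse-free status is the measure that would be affected. Sample size and analysis method do not change; Section 14 is descriptive and plans no hypothesis tests. This is a minor internal inconsistency in dispensing and visit text, not a flawed design choice. It is worth correcting because it touches treatment continuity and the correction is cheap.

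**What to change.** Make Section 9.6 and Table 2 list the same visits, then bring Section 8.1 into line.

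- **If Table 2 stands:** list its visits in Section 9.6 and state that the last on-treatment interval is 12 weeks. In Section 8.1, either exempt the W40 dispensing from the cap so that it covers the whole interval, or provide a pharmacy refill without a clinic visit. The exempted quantity is up to 92 tablets if dosing runs to the W52 visit (368 − 276), or 88 if it stops at day 364 (364 − 276). Time the refill from the actual W40 visit, within 56 days of it, because a subject seen early on day 276 with 56 tablets runs out on day 332.
- **If Section 9.6 stands:** add W48 to Table 2.

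It would help to define the cap in tablets at the same time; 64 covers the widest 8-week interval.

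With Table 2 kept, the cost is a text amendment plus one larger dispensing or one refill for each subject still on drug at W40. Adding W48 costs one more visit, with its standard laboratory tests, per such subject. For subjects already past W40, report days without drug between W40 and W52 from the existing diary.
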